9.3 SUMMARY OF FINDINGS FROM PRE-CLINICAL STUDIES

Endocine and Immunose FLU have been extensively studied and characterised in mice, rats, and ferrets. Endocine significantly increases both local and systemic immune responses after intranasal immunisation (Falkeborn et al., 2013). Endocine has been shown to potentiate the immune response to several different antigens and the results from studies with Immunose FLU show a broad immune response and protection from influenza disease (Maltais et al., 2014). For further details, refer to the IB.

9.4 SUMMARY OF FINDINGS FROM CLINICAL STUDIES

There is no clinical experience with Immunose FLU based on influenza split antigens and Endocine. However, there is clinical experience with Endocine using diphtheria toxoid as an antigen (dnr 151:2002/38324), human immune deficiency virus (HIV) as an antigen (CTN-BI/Vacc-4x/L3-2011/1) and most relevant using a whole inactivated influenza virus as an antigen (EUDRA CT 2007-005005-22). In total, 174 human subjects have been exposed to Endocine and the safety data support continued development. For further details, refer to the IB.

9.5 RATIONALE FOR THE STUDY DESIGN, DOSES AND CONTROL GROUPS

Immunose FLU with 2 different concentrations of Endocine will be investigated to assess the influence of adjuvant concentration on the response parameters, whereas the antigen dose will be kept constant according to standard practice for influenza vaccinations. The inactive control group (saline) is included for an enhanced interpretation of safety data through control for placebo effects, and for the analysis of immune responses through control for background antibody levels. The comparators to Immunose FLU; ██████████ for intranasal administration and ██████████ for intramuscular injection of antigen have been selected to compare the safety and tolerability and the overall immune response.

Immunose FLU will be administered at 2 occasions with a 3-week interval to maximize the magnitude of the immune response as indicated by non-clinical data. Influenza antigen without adjuvant and saline alone will also be administered nasally at two occasions. ██████████ and ██████████ will be administered at one occasion according to the prescribing information.

Endocine will be tested at the concentrations 1% and 2% in two different treatment groups. In a previous study with nasal influenza vaccination, Endocine was evaluated with concentrations ranging from 0.5% to 2% (report EV 2011-08, EUR-001). Local tolerability symptoms were more commonly reported following vaccination with Endocine compared to vaccination without Endocine with a slightly higher incidence of reactions following administration of 2% compared to 0.5% and 1%. Symptoms were rapidly reversible and there were no safety concerns for any treatment group. In the present study the dose-response for Endocine versus safety variables and immune response will be evaluated, and the dose steps 1% and 2% are considered adequate.

The immunology variables to be investigated in the study have been selected to represent both systemic and local immune responses, which both might be indicative of the protective efficacy in later studies.

Administration site reactions will be collected at the clinic during 2 hours of observation after each study drug administration. In previous studies with Endocine products such reactions, if occurring, were transient and in the vast majority of cases disappeared within this time period. Possible later local and systemic reactions will be collected over 10 days using a diary. In accordance with the guidelines on influenza vaccines and adjuvanted vaccines a long-term safety follow-up for 6 months after the last vaccination is included to detect any potential late occurring immune-mediated diseases (IMDs) that may be associated with the vaccination.

9.5.1 Choice of comparators

██████████ is considered the best injectable comparator available for this study although it only contains three influenza strains while the other test products (including ██████████) contain four strains. The three strains included in ██████████ are the same as in the test products (group 1-3) and the antigens have been manufactured at the same site (██████████).

The difference between trivalent influenza vaccines (TIV) and QIV is that the latter contains one extra influenza strain (an additional influenza B-strain). This extra strain is, as all other strains, chosen yearly by the WHO.

Several clinical studies (Cadorna-Carlos et al., 2015, Kieninger et al., 2013) have been performed showing that safety including solicited reactions, unsolicited adverse events (AEs) and serious AEs (SAEs) are similar for TIV and QIV. QIV vs TIV has shown superior immunogenicity for the additional B strain without interfering with immune responses to shared strains.

██████████ is considered the best intranasal comparator for this study as it will allow comparison of local tolerability at the administration site and local immune responses (nasal IgA).

Several studies have shown that [REDACTED] may have some efficacy in adults (see Appendix 3). However, a conclusion on clinical benefit of this vaccine in adults could not be made, given that results observed in some studies versus injectable influenza vaccines were suggestive of a lower efficacy of [REDACTED]. For this reason, [REDACTED] is only indicated for children from 24 months to less than 18 years of age according to the EMA. However, [REDACTED] is not contraindicated in healthy adults and the same vaccine is sold under the trade name [REDACTED] in the United States is approved by the FDA for use in persons 2 to 49 years.

9.6 RISK-BENEFIT ASSESSMENT

Vaccination to protect against influenza has been used extensively over many decades and is recommended by the WHO to pregnant women, healthcare workers, children 6 to 59 months, the elderly and those with high-risk conditions. Subjects with known severe allergies to any of the vaccine products or a history of Guillain-Barré Syndrome within 6 weeks of previous influenza vaccination will be excluded from the present study. Nasal administration of LAIV is not recommended for pregnant women or immunosuppressed adults and these groups will therefore not be enrolled in the study.

Endocine has been investigated in 3 previous clinical studies with antigens from diphtheria, influenza and HIV and has been administered to a total of 174 subjects. Adverse drug reactions have been restricted to transient local reactions at the administration site. No safety concerns have been identified in these studies.

An increased risk of narcolepsy was found following vaccination with the pandemic influenza vaccine Pandemrix that was specifically produced for pandemic 2009 H1N1 influenza. The increased incidence of narcolepsy was the highest in children and adolescents (20 years and younger) and declined gradually with age up to approximately 30 years of age. No increase in narcolepsy incidence has been observed in conjunction with seasonal influenza vaccination in Sweden 2010-2011 as reported by the medical products agency (MPA). The Immunose FLU vaccines in the present study contain inactivated split influenza antigens that are active ingredients in a seasonal influenza vaccine [REDACTED]. The prescribing information of [REDACTED] and of [REDACTED] have no mentions of narcolepsy as a reported adverse reaction. Based on available information and recommendations it is assessed that there is no increased risk of developing narcolepsy when participating in the present study.

Subjects will remain at the clinic for at least 2 hours after administration for observation of local and systemic reactions by medical staff. The Investigator will ascertain that adequate facilities and procedures are available to handle emergency situations should they occur during the study. Study specific assessments and sampling procedures like blood pressure measurements and frequent blood sampling can cause transient discomfort but the risk is deemed to be low and ethically justifiable.

The design of the study will ensure that any aforementioned risk factor is minimised whilst the scientific and medical goals for the study will be fulfilled so that the inclusion of healthy volunteers in the study is ethically justifiable.

Possible benefits for the subjects include a thorough health evaluation and an influenza vaccination for subjects randomised to a treatment group where influenza vaccine is given. The treatments will be performed before the expected outbreak of influenza in the 2016/2017 season and may provide protection against the infection.

10. OBJECTIVES

10.1 PRIMARY OBJECTIVE

To evaluate the safety and tolerability of Immunose FLU based on Endocine and quadrivalent influenza antigen.

10.1.1 Primary endpoints

- Type and incidence of AEs and SAEs from the time of first study drug administration (Visit 2) until the last visit to the clinic (Visit 4 for group 1 to 4 and Visit 3 for group 5 to 6).
- Type and incidence of SAEs and AEs of special interest during the 6 months safety follow-up.
- Frequency and severity of administration-site reactions as assessed by an independent evaluator with help from study subject before study drug administration and 15 minutes and 120 minutes after study drug administration. Administration-site reactions to be recorded are swelling, redness, pain and pruritus in the administration area (nose or arm). Reactions are classified as none, mild, moderate or severe. The administration-site reactions pain and pruritus will also be recorded by the subject in an electronic diary for 10 days starting in the evening the day after each treatment and classified as none, mild, moderate or severe.
- Frequency of solicited AEs. The subjects will record the occurrence of solicited AEs in an electronic diary for 10 days after study drug administration. Solicited AE include runny nose, nasal congestion, sneezing, fever (i.e., temperature >38°C), chills, sweating, headache, tiredness, muscle aches, joint pain, cough, sore throat, nausea.
- Frequency of clinically significant changes in ECG, vital signs, physical examination findings and laboratory variables from baseline to the last visit to the clinic.

10.2 SECONDARY OBJECTIVE

To evaluate the immune response to Immunose FLU based on Endocine and quadrivalent influenza antigen by measurement of HI and VN titres.

10.2.1 Secondary endpoints

- Measurement of haemagglutination-inhibition (HI) in blood, including:
 - Geometric mean titres (GMTs) and pre-/post-treatment ratios (GMRs)
 - Percentage of subjects with seroprotection (i.e., an HI titre ≥ 40) at Day 21 and for group 1-4 also at Day 42.
 - Percentage of subjects with seroconversion (i.e., either a pre-treatment HI titre < 10 and a post-treatment titre ≥ 40 or a pre-treatment HI titre ≥ 10 and a fourfold increase in titre) at Day 21 and for group 1-4 also at Day 42.
- Measurement of virus neutralization (VN) titres in blood (pre-treatment and 21 days after each treatment)
 - GMTs and pre-/post-treatment GMRs

10.3 EXPLORATORY OBJECTIVE

To evaluate the immune response to Immunose FLU based on Endocine and quadrivalent influenza antigen by measurement of immunoglobulin A (IgA) in nasal secretions.

10.3.1 Exploratory endpoints

- Measurement of influenza-specific immunoglobulin A (IgA) in nasal secretions (pre-treatment and 21 days after each treatment)

10.3.1.1 Post-hoc exploratory endpoints

The following may be analysed if considered valuable based on the results of the secondary analyses:

- Influenza-specific T cell responses
- Single radial haemolysis (SRH) analysis
- Functional analysis of IgA in nasal swab
- Measurement of neuraminidase (NA) specific antibodies

Exploratory analyses may only be performed on selected subjects, time points and virus strains but will always be performed both pre-and post-treatment. Results from the analyses of exploratory endpoints may be presented separate from the clinical study report (CSR).

11. STUDY DESIGN

This is a Phase I/II, randomised, partially double-blind (group 1 to 4), parallel-group study designed to evaluate the safety, tolerability and immune response following Immunose FLU vaccination at 2 sites in Sweden.

Consenting subjects will be assessed for eligibility at the screening visit (Visit 1) within 6 weeks prior to randomisation. Eligibility will be re-confirmed prior to each dose.

A total of 162 subjects will be randomised to one of 6 treatment groups in a 2:2:2:1:1:1 ratio on Day 0 (Visit 2) as follows:

- **Group 1:** Immunose FLU 1%, containing 15 µg HA/strain and 1% Endocine for intranasal administration (n=36)
- **Group 2:** Immunose FLU 2%, containing 15 µg HA/strain and 2% Endocine for intranasal administration (n=36)
- **Group 3:** Influenza antigen, containing 15 µg HA/strain for intranasal administration (n=36)
- **Group 4:** Saline (NaCl) for intranasal administration (n=18)
- **Group 5:** ██████████, containing 15 µg HA/strain for intramuscular administration (n=18)
- **Group 6:** ██████████, containing $10^{7.0\pm 0.5}$ FFUs for intranasal administration (n=18)

Subjects in group 1 to 4 will receive treatment in a partially double-blinded fashion via intranasal administration on Day 0 (Visit 2) and on Day 21+7 (Visit 3), see Table 1. Since the visual appearance of the study drugs may differ, there is a risk that the administering nurse will be unblinded. Therefore the pre- and post-treatment inspection of the administration site will be performed by an independent evaluator. The same independent evaluator will perform both pre- and post-dose assessments. For further details on blinding, refer to Section 13.10.

For subjects in group 1 to 4 there will be a total of 4 visits to the clinic; Visit 1 (screening), Visit 2 (Day 0), Visit 3 (Day 21+7) and Visit 4 (Day 42+7). Telephone contacts will be taken approximately every 8th week after the last visit to the clinic (Visit 4) for collection of any AEs of special interest or SAEs that may have occurred after Visit 4 during a 6 months safety follow-up period starting from the day of the last vaccination. For details on the follow-up phase, refer to Section 15.3.11.

Subjects in group 5 and 6 will receive treatment in an unblinded fashion via a single intramuscular (group 5) or single intranasal (group 6) administration on Day 0 (Visit 2), see Table 3. No treatment will be given on Day 21+7 (Visit 3).

For subjects in group 5 and 6 there will be a total of 3 visits to the clinic; Visit 1 (screening), Visit 2 (Day 0), and Visit 3 (Day 21+7). Telephone contacts will be taken approximately every 8th week after the last visit to the clinic (Visit 3) for collection of any AEs of special interest or SAEs that may have

occurred after Visit 3 during a 6 months safety follow-up period starting from the day of the last vaccination.

In all groups, safety and tolerability, including local tolerability, will be assessed. Local tolerability (swelling and redness [assessed by the independent evaluator] and pain and pruritus [assessed by the subject]) will be assessed before and after each treatment with study drug (Visit 2 and 3 for group 1 to 4 and Visit 2 for group 5 to 6). Safety and tolerability will be assessed by vital signs (blood pressure and heart rate), physical examination, 12-lead electrocardiogram (ECG), collection of AEs and laboratory tests (haematology, clinical chemistry and urinalysis) at time points specified in Table 1 to Table 4. Subjects with suspected influenza will be tested to confirm presence and strain of the influenza virus.

Local tolerability will also be assessed by the subjects' recording of the presence or absence of local administration site reactions (pain and pruritus) and solicited AEs (runny nose, nasal congestion, sneezing, fever [temperature >38°C], chills, sweating, headache, tiredness, muscle aches, joint pain, cough, sore throat, nausea) in an electronic diary for 10 days after each dosing occasion, starting in the evening the day after treatment.

[figure not shown]
Immune responses against the vaccine antigens will be evaluated in both nasal and blood samples. Influenza-specific immune responses will be evaluated in nasal samples (IgA) and in serum (HI and VN) and PBMC (T-cells) from blood samples. Blood samples for peripheral blood mononuclear cell (PBMC) preparation and subsequent T-cell analysis will be taken from 10 subjects per treatment group at the same time points as the other immunology blood samples. Sampling for immunology analyses at visits and time points specified in Table 1 to Table 4.

The total study duration for the subjects in the study will be up to 36 weeks (group 1 to 4) and 33 weeks (group 5 and 6) including a 6 week screening period and a 180 days follow-up period after the last vaccination.

Further details on the investigational medicinal products are provided in Section 13.1. Procedures for maintaining the blind is described in Section 13.10. Randomisation procedures are outlined in Section 13.7.

Safety assessments are described in detail in Section 15 and efficacy assessments are described in Section 16.

Figure 1 Study flowchart and blood sampling schedule

¹ Telephone follow-up approximately every 8th week ±7 days following the last visit to the clinic for a total of 3 occasions during 180 days starting after the last vaccination.

² Nasal swab for group 1 to 4 at Visit 3 will be performed at least 60 minutes prior to the pre-dose administration site inspection for local tolerability assessments.

Table 1 Schedule of events group 1 to 4

Day (+/- visit window) Week (+/- visit window)	Visit 1 Screening	Visit 2	Visit 3 ¹	Visit 4 ¹	Safety follow-up (telephone calls)		
	Day -42 to Day -1 Week-6 to week-1	Day 0 Week 0	Day 21 (+7) Week 3 (+1 week)	Day 42 (+7) Week 6 (+ 1 week)	Day 81±7 Week 11 (±1 week)	Day 141±7 Week 20 (±1 week)	Day 201 ±7 Week 28 (±1 week)
Informed consent	X						
Eligibility criteria ²	X	X ²	X ²				
Demographics	X						
Medical history	X						
Physical examination	X			X			
Weight and height	X						
Electrocardiogram (ECG)	X			X			
Pregnancy test (urine dipstick) ³	X ³	X ³	X ³				
HIV, Hepatitis B and C blood sampling	X						
Urine drug screen	X						
Haematology and clinical chemistry blood sampling	X			X			
Urinalysis sampling	X			X			
Prior and concomitant medications	X	X	X	X			
Randomisation		X					
Diary instructions		X					
Diary check-up							
AEs ^{4,5}		X ⁴	X	X	X ⁵	X ⁵	X ⁵
Vital signs ⁶	X	X ⁶	X ⁶	X			
Nasal swab ⁷	X		X ⁷	X			
Immunology blood sampling ⁸		X ⁸	X ⁸	X ⁸			
Administration site inspection for local tolerability ⁹		X ⁹	X ⁹				
Dose administration ¹⁰		X ¹⁰	X ¹⁰				

¹ At least 3 weeks between Visit 2 and Visit 3 and between Visit 3 and Visit 4.

² Continued eligibility criteria are defined in Section 12.6.

³ Pregnancy test should be performed in females at screening and pre-dose at Visit 2 and Visit 3.

⁴ Pre-treatment events will be collected from signing of the ICF until first dose and AEs will be collected post study drug administration.

⁵ SAEs and AEs of special interest (Section 14.1.5).

⁶ Recording of vital signs (heart rate and blood pressure) should be performed prior to dosing and at 30 minutes and 120 minutes post study drug administration (before the subject leaves the clinic). Temperature should be measured prior to each dosing occasion.

⁷ Nasal swab for IgA analysis should be performed at least 60 minutes prior to the pre-dose assessment of local tolerability at Visit 3. Instructions are provided in Section 16.1.

⁸ Blood sampling for serum from all subjects and blood sampling for PBMC preparation and T-cell analysis as randomized (10 subjects per group).

⁹ Assessment of local tolerability parameters should be performed prior to dosing and at 15 and 120 minutes post-study drug administration according to specific instructions (Section 15.1).

¹⁰ Nasal study drug administration according to specific instructions (Section 13.5.1).

Table 2 Timing of assessments on treatment days group 1 to 4

Time point	Assessment	Visit 2	Visit 3	Comment
Pre-dose	Continued eligibility criteria	X ¹	X	
	Pregnancy test (urine dipstick)	X ¹	X	
	Vital signs including body temperature	X ¹	X	
	Concomitant medications	X ¹	X	
	Randomisation	X		
	Diary check-up		X	
	Pre-treatment events/AEs	X	X	
	Nasal swab for IgA analysis		X	At least 60 minutes before local tolerability assessments at Visit 3
	Immunology blood sampling	X	X	
Local tolerability assessments	X ²	X ²	By independent evaluator ²	
0	Dose administration	X	X	
15 min +5min	Local tolerability assessments	X ²	X ²	By independent evaluator ²
30 min ±5 min	Vital signs	X	X	
120 min ±5 min	Local tolerability assessments	X ²	X ²	By independent evaluator ² Timing of local tolerability assessment is prioritised over timing of vital signs assessments
120 min ± 20 min ³	Vital signs	X ³	X ³	
Post-dose	AEs	X	X	
	Diary instructions	X	X	

¹ Prior to randomisation.

² The same evaluator should perform the pre- and post-dose assessments.

³ Taken before the subject leaves the clinic.

Table 3 Schedule of events group 5 and 6

Day (+/- visit window) Week (+/- visit window)	Visit 1 Screening	Visit 2	Visit 3 ¹	Safety follow-up (telephone calls)		
	Day -42 to Day -1 Week-6 to week -1	Day 0 Week 0	Day 21 (+7) Week 3 (+1 week)	Day 60±7 Week 8 (±1 week)	Day 120±7 Week 17 (±1 week)	Day 180±7 Week 26 (±1 week)
Informed consent	X					
Eligibility criteria	X	X ²				
Demographics	X					
Medical history	X					
Physical examination	X		X			
Weight and height	X					
Electrocardiogram (ECG)	X		X			
Pregnancy test (urine dipstick) ³	X ³	X ³				
HIV, Hepatitis B and C blood sampling	X					
Urine drug screen	X					
Haematology and clinical chemistry blood sampling	X		X			
Urinalysis sampling	X		X			
Prior and concomitant medications	X	X	X			
Randomisation		X				
Diary instructions		X				
Diary check-up						
AEs ^{4,5}		X ⁴	X			
Vital signs ⁶	X	X ⁵	X	X ⁵	X ⁵	X ⁵
Nasal swab ⁷	X	X ⁶	X ⁶			
Immunology blood sampling ⁸		X ⁸	X ⁸			
Administration site inspection for local tolerability ⁹		X ⁹				
Dose administration ¹⁰		X ¹⁰				

¹ At least 3 weeks between Visit 2 and Visit 3.

² Continued eligibility criteria are defined in Section 12.6.

³ Pregnancy test should be performed in females at screening and pre-dose at Visit 2.

- ⁴ Pre-treatment events will be collected from signing of the ICF until first dose and AEs will be collected post study drug administration.
- ⁵ SAEs and AEs of special interest (Section 14.1.5).
- ⁶ Recording of vital signs (heart rate and blood pressure) should be performed prior to dosing and at 30 minutes and 120 minutes post study drug administration (before the subject leaves the clinic). Temperature should be measured prior to each dosing occasion.
- ⁷ Nasal swab for IgA analysis according to specific instructions (Section 16.1).
- ⁸ Blood sampling for serum from all subjects and blood sampling for PBMC preparation and T-cell analysis as randomized (10 subjects per group)
- ⁹ Assessment of local tolerability parameters should be performed prior to dosing and at 15 and 120 minutes post-study drug administration according to specific instructions (Section 15.1).
- ¹⁰ Nasal or intramuscular study drug administration according to the manufacturers' instructions.

Table 4 Timing of assessments on treatment day group 5 and 6

Time point	Assessment	Visit 2	Comment
Pre-dose	Continued eligibility criteria	X ¹	
	Pregnancy test (urine dipstick)	X ¹	
	Vital signs including body temperature	X ¹	
	Concomitant medications	X ¹	
	Pre-treatment events	X	
	Randomisation	X	
	Immunology blood sampling	X	
	Local tolerability assessments	X ²	By independent evaluator ²
0	Dose administration	X	
15 min +5min	Local tolerability assessments	X ²	By independent evaluator ²
30 min ±5 min	Vital signs	X	
120 min ±5 min	Local tolerability assessments	X ²	By independent evaluator ² Timing of local tolerability assessment is prioritised over timing of vital signs assessments
120 min ±20 min³	Vital signs	X ³	
Post-dose	AEs	X	
	Diary hand-out and instructions	X	

¹ Prior to randomisation.

² The same evaluator should perform the pre- and post-dose assessments.

³ Taken before the subject leaves the clinic.

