13.5 DOSES AND TREATMENT REGIMENS

13.5.1 Doses and treatment regimens group 1 to 4 (test products)

The test products (Immunose FLU, influenza antigen and saline, respectively) will be administered in 2 doses delivered at least 3 weeks apart. Up to 4 weeks between administrations is allowed.

A short instruction for nasal administration of Immunose FLU, influenza antigen and saline is provided below and a complete instruction is provided separately.

Prior to administration, the content of each vial should be mixed carefully. Upon administration, the subject should sit in an upright position and lean the head backwards (Figure 2 and Figure 3). A calibrated pipette and pipet tips must be used.

A total of 150 µl of IMP should be administered in each nostril. The nose drops must be applied on the upside nasal cavity.

Figure 2 Head position of subject upon nasal administration of test products (group 1 to 4)

Figure 3 Administration of test products (group 1 to 4)

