15.3 ADVERSE EVENTS

Any apparent side effects experienced by the subject will be assessed from the time the subject signs the informed consent and throughout the last visit to the clinic (Visit 4 for group 1 to 4 and Visit 3 for group 5 and 6).

The study personnel will document any pre-dose events, i.e. events reported after the signing of informed consent and before administration of the first dose in the medical history log of the eCRF.

The study personnel will document all AEs in the AE log of the eCRF, whether observed by the Investigator or spontaneously reported by the subject.

SAEs and AEs of special interest will be documented during the 6 months follow-up period starting after the last vaccination (Visit 3 or Visit 4).

The AE reporting period is described in Section 15.3.12.

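### The safety-call schedule appears in two incompatible forms, and the tabulated form lets the last call fall up to 14 days (Groups 1–4) or 7 days (Groups 5–6) before day 180

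*Combined protocol and SAP*

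**What the plan says.** One of the five primary endpoints in Section 10.1.1 is "Type and incidence of SAEs and AEs of special interest during the 6 months safety follow-up". Section 11 gives the length of that period as "a 180 days follow-up period after the last vaccination". Section 15.3.6 defines the adverse events of special interest (AESIs) as including potential immune-mediated diseases in this period.

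The calls are scheduled in two places, by two rules:

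- **Text.** Section 11, footnote 1 to Figure 1, and Sections 14.1.5 and 15.3.11 count about 8 weeks at a time from the last clinic visit. The footnote reads "Telephone follow-up approximately every 8th week ±7 days following the last visit to the clinic for a total of 3 occasions during 180 days", and the two later sections also give ±7 days and three occasions. The footnote ties its overall limit to the last dose: "for a total of 3 occasions during 180 days starting after the last vaccination".
- **Tables.** Tables 1 and 3 print study days. The last call is at "Day 201 ±7 Week 28 (±1 week") for Groups 1–4 and at "Day 180±7 Week 26 (±1 week") for Groups 5–6.

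Table 1 allows Visit 3, the second dose, on Day 21 with a window of +7 days, and Section 13.5.1 agrees: "Up to 4 weeks between administrations is allowed".

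Section 15.3 describes the follow-up as "starting after the last vaccination (Visit 3 or Visit 4"). Those are the last clinic visits of the two sets of groups, not their last vaccinations. Inclusion criterion 6 in Section 12.4 places the last vaccination at Visit 3 (Groups 1–4) and Visit 2 (Groups 5–6).

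No section says that the final call must not precede day 180. Section 18.5.2 gives no onset cut-off for events in this period.

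**The concern.** The endpoint has a stated length and a stated starting point, and the calls are the means by which subjects are asked about it. Two things follow if the calls are not tied to that starting point. Site staff may work to different schedules, depending on whether they read the text or the table. And the last call may come before the window has closed, with no later contact described.

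Section 9.5 says the follow-up is there to detect late immune-mediated disease, so the end of the window matters. At stake is whether every subject is asked about the full period that the report will state.

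**Working it through.** **Inputs.** Dose 2 (Visit 3): Day 21 to 28. Visit 4: Day 42 to 49, at least 21 days after Visit 3 (Table 1, note 1). Groups 5–6: only dose on Day 0, last clinic visit on Day 21 to 28 (Table 3). Call windows ±7 days. Screening up to 42 days.

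**1. The plan's own figure.** Last call minus last vaccination at nominal days: 201 − 21 = 180 (Table 1) and 180 − 0 = 180 (Table 3). The stated 180 days is reproduced. The table days are the nominal last vaccination plus 60, 120 and 180. Counted from the nominal last clinic visit, the steps are 39, 60 and 60 days, not 56, 56 and 56.

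**2. Text against tables, nominal visits.** Text call k = last clinic visit + 56k.

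| Groups | Call | Text window | Table window | Days in common |
|---|---|---|---|---|
| 1–4 | 1 | 98 ± 7 = 91–105 | 81 ± 7 = 74–88 | none |
| 1–4 | 2 | 154 ± 7 = 147–161 | 141 ± 7 = 134–148 | 147–148 |
| 1–4 | 3 | 210 ± 7 = 203–217 | 201 ± 7 = 194–208 | 203–208 |
| 5–6 | 1 | 77 ± 7 = 70–84 | 60 ± 7 = 53–67 | none |
| 5–6 | 2 | 133 ± 7 = 126–140 | 120 ± 7 = 113–127 | 126–127 |
| 5–6 | 3 | 189 ± 7 = 182–196 | 180 ± 7 = 173–187 | 182–187 |

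If the last clinic visit is 7 days late, the text windows move 7 days later and no call has any day in common.

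**3. Days from last vaccination to last call.**

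- Table 1: earliest 194 − 28 = 166, latest 208 − 21 = 187. Largest shortfall 180 − 166 = 14 days (14/180 = 7.8%).
- Table 3: 173 to 187. Largest shortfall 7 days (7/180 = 3.9%).
- A Table 1 call made exactly on Day 201 is 1 to 7 days short when dose 2 was on Days 22 to 28 (201 − 22 = 179; 201 − 28 = 173).
- Text rule, both sets of groups: (21 to 28) + 168 ± 7 = 182 to 203.

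**4. Share of subjects short.** The documents do not give it. If every visit and call is on its nominal day, it is 0%. Under an assumed uniform spread over the windows, it is 7/15 = 47% in Groups 5–6. In Groups 1–4, (8 + 7 + … + 1)/120 = 36/120 = 30% reach 180 days, so 70% do not; the mean shortfall is 504/120 = 4.2 days over all subjects. With all second doses on Day 21 the figure is 47%; with all on Day 28 it is 14/15 = 93%.

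**5. Do the stated durations settle which schedule is meant?** No. The table maxima are (42 + 208)/7 = 35.7 and (42 + 187)/7 = 32.7 weeks. The text at nominal visits gives (42 + 42 + 168)/7 = 36.0 and (42 + 21 + 168)/7 = 33.0 weeks. Both fit the stated 36 and 33.

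**6. Other readings.** If the Table 1 calls were meant to move with the actual second dose, the lower bound would be 173 days; the table does not say so. If the label Week 28 governs (28 × 7 = 196), it would be 196 − 7 − 28 = 161. If the text's ±7 days applied to each interval in turn, the text range would widen to 21 + 3 × 49 = 168 through 28 + 3 × 63 = 217.

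**The case against.** The strongest reply is that this is a scheduling untidiness around a design that works. The nominal tables give exactly 180 days. A symmetric ±7-day window for a telephone call is a legitimate choice, and 166 days needs two extremes at once: dose 2 on Day 28 and a call 7 days early. The text speaks only of approximate 8-week steps. Section 15.3.9 requires serious adverse events (SAEs) to be reported within 24 hours of awareness from the first dose on, with no end date there. Section 14.1.5 asks about the time since the previous contact, so a call later than day 180 still covers the window. The visit numbers in Section 15.3 look like a slip and contribute nothing to the shortfall.

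Most of this stands. A call after day 180 is no loss of information, so the footnote's 180-day limit is a wording conflict only. The SAE rule means that the gap mainly concerns non-serious AESIs, which are described as collected through the calls.

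Two things are not answered. The first-call windows do not overlap, and the word approximately cannot absorb that when ±7 days stands beside it. And a late second dose is allowed by the plan, so a call on the printed day can be early without anyone deviating.

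**Conclusion.** The plan contradicts itself on when the calls are made, and the tabulated version can end solicited collection before its own day 180: by at most 14 days in Groups 1–4 and 7 days in Groups 5–6. This rests on Table 1 counting from Day 0, as printed. It should be corrected, but it is a limited gap at the end of a descriptively analysed endpoint.

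Four stronger readings are tempting and are not supported:

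- *Many subjects will be cut short.* The share ranges from 0% to 93% in Groups 1–4 across the timings tried, and the documents do not give the timing.
- *The contradiction causes the shortfall.* It does not: with ±7 days around each target, the text rule reaches at least 182 days. The shortfall comes from the table windows and the Day 0 anchor.
- *Section 19.7 closes each subject at the last call.* It defines the end of the follow-up part for the study as a whole. What is true is that no later contact is described.
- *Group comparisons are biased.* Groups 1–4 share one schedule, so the adjuvant, antigen-alone and saline contrasts are not disadvantaged by design. Against the open-label Groups 5–6, the mean shortfall under the uniform assumption differs by 4.2 − 1.9 = 2.3 days (28/15 = 1.9 in Groups 5–6), or 1.3% of 180.

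**What to change.** Reconcile footnote 1 to Figure 1, Sections 11, 14.1.5 and 15.3.11, and Tables 1 and 3 to one schedule, as follows:

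- Count all three calls from each subject's actual last vaccination date.
- Allow the final call only on or after the plan's own day 180, for example day 180 with a window of +14 days.
- State that events count if their onset is on or before day 180, whenever the call is made.
- Correct the visit numbers in Section 15.3 to agree with the dosing visits.
- Restate the maximum duration. With a +14-day window it becomes 42 + 28 + 194 = 264 days (37.7, about 38 weeks) for Groups 1–4 and 42 + 194 = 236 days (33.7, about 34 weeks) for Groups 5–6, in place of 36 and 33.

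The number of calls does not change. The last call comes up to about two weeks later for some subjects. Because the stated duration rises by one to two weeks, the subject information may need a small update, with approval under Section 19.4 where that applies.
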